The DAS28 is a composite index for measuring disease activity in RA and is calculated at each study visit. The index includes swollen (range 0-28) and tender joint counts (range 0-28), acute phase response erythrocyte sedimentation rate (ESR), and general health status (range 1-100). The DAS28, which uses a 28 joint count including shoulders is derived from the original DAS, which includes a 44 swollen joint count. The DAS28 has been validated in RA. The index is calculated using the formula from the EULAR website: <http://emeunet.eular.org/links.cfm?catID=19>.

The DAS28 ranges from 0 to 9.3, where higher scores represent higher disease activity.

Joint Tenderness and Swelling Assessments

An assessor at each site will be used to evaluate tenderness and swelling of the 28 joints specified by the DAS28 scoring system. Scoring for each joint will be based on whether or not the joint is swollen (1=yes, 0= no) and whether the joint is tender (1=yes, 0= no). The CRF will also have the options Not done and Not Evaluable. Evaluations will be done at all study visits.

Health Assessment Questionnaire (HAQ)

The HAQ is a patient-reported outcomes (PRO) questionnaire based on 5 patient-centered dimensions; disability, pain, medication effects, costs of care, and mortality. The version used for this trial is the “short” or 2-page HAQ comprised of the HAQ disability module and the global and pain visual analog scales [20]. The HAQ may be completed directly by the subject or by an interviewer. HAQ will be collected at Baseline and all post dose study visits. [Appendix 14.2]

Short Form-36 (SF-36) Survey

The Short Form (36) Health Survey is a patient-reported survey of patient health [21]. The SF-36 is a measure of health status. SF-36 surveys may be completed directly by the subject or by an interviewer. SF-36 surveys will be collected at Baseline and Week 1, 2, 4, 6, and 12.

[Appendix 14.1]

Functional Assessment of Chronic Illness Therapy (FACIT) Score

"FACIT" (Functional Assessment of Chronic Illness Therapy) was adopted as the formal name of the measurement system in 1997 to portray the expansion of the familiar "FACT" (Functional Assessment of Cancer Therapy) questionnaires into other chronic illnesses and conditions [22]. Questionnaires may be completed directly by the subject or by an interviewer. The FACIT questionnaire will be collected at Baseline, Week 4 and Week 6.

[Appendix 14.3]

EULAR Response

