Comparing the DAS28 from one patient on two different time points, it is possible to define moderate or good response [14]. The EULAR response criteria are defined as follows:

DAS28 improvement →	> 1.2	> 0.6 and ≤ 1.2	≤ 0.6
Present DAS28↓			
≤ 3.2	good response	moderate response	no response
> 3.2 and ≤ 5.1	moderate response	moderate response	no response
> 5.1	moderate response	no response	no response

The EULAR response will be calculated at all visits after Baseline.

American College of Rheumatology 20/50/70 (ACR 20/50/70)

ACR score is a scale to measure change in rheumatoid arthritis symptoms. It is named after the American College of Rheumatology. Different degrees of improvement are referred to as ACR20, ACR50, ACR70. The following definition of improvement was selected: 20% improvement in tender and swollen joint counts and 20% improvement in 3 of the 5 remaining ACR core set measures: patient and physician global assessments, pain, disability, and an acute-phase reactant [23]. ACR 50 and ACR 70 criteria are defined in a manner similar to that for ACR 20, but with improvement of at least 50 percent and 70 percent in the individual measures, respectively.

Visual Analog Scale (VAS)

The visual analogue scale or visual analog scale (VAS) is a psychometric response scale which can be used in questionnaires. It is a measurement instrument for subjective

characteristics or attitudes that cannot be directly measured. When responding to a VAS item, respondents specify their level of agreement to a statement by indicating a position along a continuous line between two end-points. Four VAS measurements will be at each study visit; the subject will assess their current pain level and general health, the subject will assess their RA Activity levels, and a trained blinded site evaluator will independently assess the subjects RA Activity levels.

Subjects will be given an explanation on use of different scales at screening.

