4.3 Baseline Definition

For all variables, baseline will be considered to be the last value obtained prior to first start of treatment, and may be on Screening or on Day 1, dependent on parameter. Change from baseline will be the difference between the value at a given time point and the baseline value.

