4.8.3 Other Secondary Analyses

All other secondary analyses will be completed for both the ITT and PP populations. EULAR response (good, moderate, no response) at Week 1, 2, 3, 4, 6, 8 and 12 will be summarized by treatment group and the treatment groups will be compared by using the non-parametric Wilcoxon-Mann-Whitney test.

DAS28 will be summarized and analyzed at Week 1, 2, 3, 4, 6, 8 and 12. The DAS28 score is calculated as follows:

$$DAS28 = (0.555 \times \sqrt{TJC}) + (0.284 \times \sqrt{SJC}) + (0.7 \times \log_e ESR) + (0.0142 \times GH)$$

where TJC = tender joint counts on 28 joints, SJC = swollen joint counts on 28 joints, GH = general health, i.e. patient's global assessment of disease activity (100 mm VAS) and ESR = erythrocyte sedimentation rate (mm/hr). If ESR was not available, then CRP may be used instead. See Appendix C for details on scoring and coding. At a particular timepoint, if one or more of the four components used in calculating DAS28 are missing, then the DAS28 will be considered missing at that timepoint.

If DAS28 scores are approximately normally distributed via visual inspection, then DAS28 scores at 1, 2, 3, 4, 6, 8 and 12 weeks will be analyzed using analysis of covariance (ANCOVA), including baseline scores and study site as covariates. If DAS28 scores are markedly non-normally distributed via visual inspection, then the Kruskal-Wallis test will be used to compare the groups at each time point. In addition to the group comparison, the time course of DAS28 scores will be submitted to a repeated measures analysis of variance, with treatment group, time and the interaction of treatment group and time in the model.

If the percentage change in DAS28 scores is approximately normally distributed via visual inspection, then % change at 1, 2, 3, 4, 6, 8 and 12 weeks will be analyzed using ANCOVA, including baseline scores and study site as covariates. If % change is markedly non-normally distributed via visual inspection, then the Kruskal-Wallis test will be used to compare the groups at each time point. In addition to the group comparison, the time course of % change will be submitted to a repeated measures analysis of variance, with treatment group, time and the interaction of treatment group and time in the model.

Time to first EULAR response (moderate or good) will be analyzed using the Kaplan-Meier method; comparison between the treatment groups will be performed using the log-rank test.

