Listing 21.B	Adverse Events (cont'd) (SAF)
Listing 22	PK Sampling (SAF)

Figure 1 Time to First EULAR Good/Moderate Response (ITT)

8. Statistical software

SAS version 9.3 or higher will be used for all tables, listings and figures.

9. References

Biometrical Journal. 50:708-714

[figure not shown]
10. APPENDIX A – Scoring and Coding for SF-36 – Short Form 36

Details for scoring SF-36 responses can be found at:

<https://www.rand.org/health/surveys-tools/mos/36-item-short-form/scoring.html>

Associated SAS code can be found below and at:

[figure not shown]
<http://gim.med.ucla.edu/FacultyPages/Hays/utils/sf36v2-4-public.sas>

11. APPENDIX B – Scoring and Coding for EULAR

	Change in DAS28 from baseline		
DAS28 after xx weeks	>1.2	>0.6 and \leq 1.2	\leq 0.6
\leq 3.2 (inactive)	Good	Moderate	No response
>3.2 and \leq 5.1 (moderate)	Moderate	Moderate	No response
>5.1 (very active)	Moderate	No response	No response

12. APPENDIX C – Scoring and Coding for DAS28

The DAS28 is a combined index for measuring disease activity in RA. The index includes the assessment of 28 joints for swelling and tenderness, acute phase response (ESR or CRP), and general health status. The index is calculated using the following formula:

$$\text{DAS28} = 0.56 \times \sqrt{\text{TJC28}} + 0.28 \times \sqrt{\text{SJC28}} + 0.70 \times \ln(\text{ESR}) + 0.014 \times \text{VAS}$$

where

[figure not shown]
TJC28 = tender joint count on 28 joints

SJC28 = swollen joint count on 28 joints

ln = natural log

ESR = erythrocyte sedimentation rate (mm/hr)

[figure not shown]
VAS = visual analogue scale, i.e., patient's global assessment of disease activity (100 mm VAS)

13. APPENDIX D – Scoring and Coding for ACR 20/50/70

The ACR core set of outcome measures and their definition of improvement includes a $\geq 20\%$ improvement (ACR20) compared to Baseline in both SJC and TJC as well as in three out of five additional parameters: Physician's Global Assessment of disease activity VAS, patient's Global Assessment of disease activity VAS, patient's assessment of pain VAS, HAQ-DI, and acute phase reactant (either CRP or erythrocyte sedimentation rate [ESR]).

Achievement of an ACR50 requires a $\geq 50\%$ improvement in the same parameters and an ACR70 requires a $\geq 70\%$ improvement.

14. APPENDIX E – Scoring and Coding for HAQ

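### SAP Appendix B labels the EULAR response columns as change in DAS28, which under SAP 4.3 runs opposite to the improvement the protocol intends; the DAS28 coefficients are also printed at two roundings

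*Combined protocol and SAP*

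**What the plan says.** **Response rule.** The primary endpoint is the rate of good or moderate EULAR response at Day 8. SAP section 6 refers to Appendix B for its scoring. Appendix B crosses the row "DAS28 after xx weeks" (up to 3.2, above 3.2 to 5.1, above 5.1) with columns headed "Change in DAS28 from baseline". The columns are above 1.2, above 0.6 to 1.2, and at most 0.6. Good and Moderate lie only in the first two columns, and no sign convention is given.

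**Sign of change.** SAP 4.3 covers all variables: "Change from baseline will be the difference between the value at a given time point and the baseline value".

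**Protocol.** Section 8.3 prints the same table and cut-offs, but heads the columns "DAS28 improvement". It also fixes the direction of the scale: "The DAS28 ranges from 0 to 9.3, where higher scores represent higher disease activity".

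**DAS28 formula.** SAP 4.8.3 introduces its formula with "The DAS28 score is calculated as follows" and uses coefficients 0.555, 0.284, 0.7 and 0.0142, then refers to Appendix C. Appendix C says "The index is calculated using the following formula" and uses 0.56, 0.28, 0.70 and 0.014. The protocol prints no coefficients and points to an external web page.

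**The concern.** Within the SAP, the word change already has a meaning. If it is visit minus baseline, a positive value is a rise in DAS28, which is a worsening. Appendix B then attaches the response categories to the wrong side of zero. The primary endpoint, all three key secondary endpoints and time to first response depend on this table, so the rule should be correct as it stands and should not need the protocol to rescue it.

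SAP section 4 undertakes to document any difference from the protocol. SAP 4.11 lists the modifications and does not mention the new column heading.

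The two coefficient sets raise a smaller question of the same kind. EULAR categories have hard cut-offs, so two programmers who each follow the SAP could disagree on a patient close to a boundary.

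**Working it through.** The plan states no figure on this point, so there is none to reproduce.

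**1. Direction.** Each case below is scored twice with the same cut-offs: by improvement (baseline minus visit, protocol 8.3) and by change (visit minus baseline, the natural reading of SAP 4.3).

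| Baseline to visit | Improvement | Protocol table | Change | Appendix B, literal |
|---|---|---|---|---|
| 5.5 to 3.0 | +2.5 | Good | -2.5 | No response |
| 5.0 to 4.0 | +1.0 | Moderate | -1.0 | No response |
| 3.4 to 4.8 | -1.4 | No response | +1.4 | Moderate |
| 4.5 to 6.0 | -1.5 | No response | +1.5 | Moderate |
| 3.3 to 4.2 | -0.9 | No response | +0.9 | Moderate |

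Not every worsening scores as response. A move from 4.5 to 5.3 is +0.8 with a visit value above 5.1, so it remains No response.

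**2. The Good cell.** Read literally, Good needs a visit value of at most 3.2 and visit minus baseline above 1.2. Baseline must then be below 3.2 - 1.2 = 2.0. Inclusion criterion 3 requires active disease with DAS28 of at least 3.2, and eligibility is re-assessed at the baseline visit. The cell is therefore essentially unreachable, and both good-responder key secondary endpoints would be empty.

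**3. Size if coded literally.** The documents give no component distributions, so these are assumptions. Three scenarios of 500,000 simulated patients were restricted to baseline DAS28 of at least 3.2, with mean baseline DAS28 of 4.77, 5.04 and 5.29.

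- Scored as improvement, responder rates were 57.7%, 72.2% and 80.1%.
- Scored as visit minus baseline, they were 1.0%, 0.3% and 0.1%, with no Good responses.

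**4. Coefficients: bound on the score.** Appendix C minus SAP 4.8.3 equals 0.005 x sqrt(TJC) - 0.004 x sqrt(SJC) - 0.0002 x VAS. The ESR terms cancel. With joint counts from 0 to 28 and VAS from 0 to 100:

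- Maximum: 0.005 x sqrt(28) = +0.026.
- Minimum: -0.004 x sqrt(28) - 0.0002 x 100 = -0.021 - 0.020 = -0.041.

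A change score can therefore differ by at most 0.026 + 0.041, about 0.07.

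**5. Coefficients: an example flip.** Baseline is TJC 8, SJC 6, ESR 24, VAS 60. The visit is TJC 8, SJC 3, ESR 15, VAS 55.

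- SAP 4.8.3: 5.3421 - 4.7383 = 0.604, Moderate.
- Appendix C: 5.3344 - 4.7345 = 0.5999, No response.

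**6. Coefficients: frequency.** In the three scenarios above, responder status differed in 0.21%, 0.17% and 0.14% of patients, and the three-level category in 0.35%, 0.33% and 0.27%. Overall responder rates differed by at most 0.1 percentage point. A second simulation of 400,000 subjects, at assumed responder rates of 24%, 56% and 75%, gave 0.28%, 0.27% and 0.19% for responder status. Even at the planned 330 subjects, the expected number of flips is 0.0014 x 330 = 0.46 to 0.0028 x 330 = 0.92. The SAP says the study stopped early with far fewer subjects, so the actual expectation is lower.

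**The case against.** The best reply is that nobody would code the table the wrong way round. SAP 4.3 describes a difference without printing a subtraction. The protocol has the same table under an unambiguous heading, and Appendix B labels the lowest DAS28 row as inactive disease. The literal reading also defeats itself, because it empties the Good category. Since SAP 4.11 declares no change to the EULAR definition, the protocol's definition stands. All of this is right about intent, and it is why the error is unlikely to be executed. It does not make Appendix B consistent with SAP 4.3: the rule the SAP names for its primary endpoint still gives wrong categories when followed as written.

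A reader might infer that the sign problem would reverse the comparison between arms. The documents do not support that. Literal coding nearly empties the endpoint, which would be plain in the first summary table and is not a silent bias towards either treatment.

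A reader might also infer that the SAP uses two different DAS28 instruments. It does not: the Appendix C coefficients are those of SAP 4.8.3 to two significant figures. Nothing suggests that flips would favour one arm. Nor can the documents show which set matches the external page the protocol cites, so only consistency can be asked for.

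**Conclusion.** The point holds as a labelling error in an operative scoring rule, with low probability of harm and a severe effect if it were coded literally. Its basis is the natural reading of SAP 4.3 as visit minus baseline, together with the protocol's statement that higher DAS28 is worse. The collapse to 0.1-1.0% responders rests on assumed distributions. The near-impossibility of Good follows from the entry threshold alone.

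The coefficient discrepancy is a minor rounding inconsistency. The bound of about 0.04 on the score follows from the printed coefficients and the component ranges. The 0.1-0.3% of flipped responder calls depends on assumed populations. At under one expected subject, it is not expected to change the result.

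**What to change.** In SAP Appendix B, head the columns *Improvement in DAS28 (baseline minus visit value)*, matching the protocol's table. Print one coefficient set in both SAP 4.8.3 and Appendix C, and use it at baseline and at every visit. Make both corrections before unblinding, and check the program against a few worked cases such as those tabulated above.

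The cost is two text corrections and a short program check, with no new data and no change in conduct. One adjacent gap can be closed in the same edit: SAP 4.8.3 allows CRP when ESR is unavailable and refers to Appendix C, but Appendix C gives only an ESR formula. Settling the ESR coefficients does not cover that case.
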